10.3. Patient Withdrawal

Not applicable.

10.4. IRB or IEC

There must be prospective approval of the study protocol, protocol amendments, and other relevant documents (eg, ICFs, if applicable) from the relevant IRBs or IECs. All correspondence with the IRB or IEC must be retained. Copies of IRB and IEC approvals must be forwarded to Pfizer.

Before study initiation this study will undergo IRB review and clearance in the US by the CRO's IRB, RTI International Committee for the Protection of Human Subjects Research. RTI International, of which RTI Health Solutions (RTI-HS) is a business unit, holds a Federal-Wide Assurance (FWA) (#3331) from the US Department of Health and Human Services (DHHS) Office for Human Research Protections (OHRP) that allows it to review and approve protocols involving human subjects. The committee also is registered with OHRP for both DHHS- and FDA-regulated research. Our FWA requires IRB review for all studies conducted by RTI-HS that involve human subjects, regardless of the funding source or geographic location from which data are being collected. Depending on the level of risk and the nature of the research, a study may be ruled as exempt from IRB review by an IRB chair or designated IRB member. Studies that are not exempt must be approved either by an IRB chair or designated IRB member (if the study qualifies for expedited review) or by a full IRB committee.

RTI International currently has an IRB committee available to review research protocols. The committee meets monthly to review biomedical clinical trials and has appropriate medical expertise among its members. The IRB has been audited by the FDA and is fully compliant with applicable regulatory requirements. The committee reviews research studies to ensure adherence to appropriate regulations that govern human subjects research, including 45 CFR 46, 21 CFR 50 and 56, and to all applicable Helsinki Declarations and provisions of the International Council for Harmonisation of Technical Requirements for Pharmaceuticals for Human Use for conduct of multinational studies. All studies involving human subjects undergo a continuing IRB review at least once per year.

A request to classify the study as a 'non-interventional, not human data' research project will be submitted. If the IRB classifies the study as such, no additional reviews will be required.

In addition to review by RTI International's IRB, the protocol will be submitted for review and approval to the appropriate central and/or local IRBs and/or IECs. With assistance from the CRO, each principal investigator will be responsible for obtaining the necessary approval of the study protocol, protocol amendments, and ICFs (if needed), and other relevant documents, if applicable, from the central and/or local IRBs and/or IECs and for ensuring that the study complies with local legislation relating to data protection and privacy. When local approval is obtained, the documentation indicating the IRB's or IEC's (if applicable) approval and the names and qualifications of the committee members must be sent by the principal investigator to the CRO, who will send these documents to the study sponsor before the recruitment process begins.

10.5. Ethical Conduct of the Study

The study will be conducted in accordance with legal and regulatory requirements, as well as with scientific purpose, value and rigor and follow generally accepted research practices described in:

- Guidelines for Good Pharmacoepidemiology Practices (GPP) issued by the International Society for Pharmacoepidemiology (ISPE);
- Good Epidemiological Practice (GEP) guidelines issued by the International Epidemiological Association (IEA);
- Good Practices for Outcomes Research issued by the International Society for Pharmacoeconomics and Outcomes Research (ISPOR);
- Good practices for real-world data studies of treatment and/or comparative effectiveness: Recommendations from the joint ISPOR-ISPE Special Task Force on RWE in health care decision making;
- International Ethical Guidelines for Epidemiological Research issued by the Council for International Organizations of Medical Sciences (CIOMS);
- EMA European Network of Centres for Pharmacoepidemiology and Pharmacovigilance (ENCePP) Guide on Methodological Standards in Pharmacoepidemiology;
- The ENCePP Code of Conduct for scientific independence and transparency in the conduct of pharmacoepidemiological and pharmacovigilance studies;
- US FDA Guidance for Industry: Good Pharmacovigilance Practices and Pharmacoepidemiologic Assessment.

11. MANAGEMENT AND REPORTING OF ADVERSE EVENTS AND/OR ADVERSE REACTIONS

This study protocol requires human review of patient-level unstructured data; unstructured data refer to verbatim medical data, including text-based descriptions and visual depictions of medical information, such as medical records, images of physician notes, neurological scans, X-rays, or narrative fields in a database. The reviewer is obligated to report AEs with explicit attribution to any Pfizer drug that appear in the reviewed information (defined per the patient population and study period specified in the protocol). Explicit attribution is not inferred by a temporal relationship between drug administration and an AE but must be based on a definite statement of causality by an HCP linking drug administration to the AE.

The requirements for reporting safety events on the non-interventional study (NIS) Adverse-Event Monitoring (AEM) Report Form to Pfizer Safety are as follows:

- All serious and non-serious AEs with explicit attribution to **any Pfizer drug** that appear in the reviewed information must be recorded on the CRF and reported, within 24 hours of awareness, to Pfizer Safety using the NIS AEM Report Form.
- Scenarios involving drug exposure, including exposure during pregnancy, exposure during breast feeding, medication error, overdose, misuse, extravasation, lack of efficacy, and occupational exposure associated with the use of a Pfizer product must be reported, within 24 hours of awareness, to Pfizer Safety using the NIS AEM Report Form.

For these AEs with an explicit attribution or scenarios involving exposure to a Pfizer product, the safety information identified in the unstructured data reviewed is captured in the Event Narrative section of the report form, and constitutes all clinical information known regarding these AEs. No follow-up on related AEs will be conducted.

All research staff members must complete the following Pfizer training requirements:

- “*YRR Training for Vendors Working on Pfizer Studies (excluding interventional clinical studies and non-interventional primary data collection studies with sites/investigators)*”.

These trainings must be completed by research staff members prior to the start of data collection. All trainings include a “Confirmation of Training Certificate” (for signature by the trainee) as a record of completion of the training, which must be kept in a retrievable format. Copies of all signed training certificates must be provided to Pfizer. Re-training must be completed on an annual basis using the most current “Your Reporting Responsibilities” training materials.

12. PLANS FOR DISSEMINATING AND COMMUNICATING STUDY RESULTS

12.1. Results Dissemination

A final study report will be developed. Development of an abstract for presentation at a suitable conference and a study manuscript suitable for submission to an appropriate journal will be considered. All forms of dissemination will describe the rationale for the study, methods, results, and the implications of those findings.

- **Final study report:** A final study report will be developed based on analysis of the final locked dataset and will include all final study tables.
- **Abstract/poster:** In the case that results yield material suitable for generation of a conference abstract, an abstract will be prepared. If selected, the study results (either interim or final) will be used to develop a poster/presentation for the conference.
- **Peer-reviewed publication:** In the case that results yield material suitable for publication of a manuscript in a peer-reviewed journal, a manuscript will be developed. All authors will have to meet the International Committee of Medical Journal Editors (ICMJE) guidelines for authorship.

12.2. Communication of Issues

In the event of any prohibition or restriction imposed (eg, clinical hold) by an applicable competent authority in any area of the world, or if the investigator is aware of any new information which might influence the evaluation of the benefits and risks of a Pfizer product, Pfizer should be informed immediately.

ANNEX 1. LIST OF STAND ALONE DOCUMENTS

None.

ANNEX 2. ADDITIONAL INFORMATION

Not applicable.

## LIST OF ABBREVIATIONS

Abbreviation	Definition
AE	adverse event
CI	confidence interval
EDC	electronic data capture
EMA	European Medicines Agency
ER	emergency department
EU	European Union
FU	follow-up
HCRU	health care resource utilization
ICD-10	International Classification of Diseases, Tenth Edition
ICD-9	International Classification of Diseases, Ninth Edition
ICU	intensive care unit
KM	Kaplan-Meier
PRISMA	Patterns of Real-World Isavuconazole Use, Effectiveness, Safety, and Health Care Resource Utilization
RWE	real-world evidence
SAE	serious adverse event
SAP	statistical analysis plan
TDM	therapeutic drug monitoring
UK	United Kingdom

PFIZER CONFIDENTIAL

CT24-WI-GL03-RF03 1.0 *Non-Interventional Statistical Analysis Plan For Secondary Data Collection*  
*Study 16-Sep-2020*  
 Page 4 of 19

## 1 INTRODUCTION

Note: in this document any text taken directly from the non-interventional study protocol is *italicized*.

### 1.1 STUDY BACKGROUND

*Invasive aspergillosis and mucormycosis are rare, life-threatening fungal infections associated with high mortality. Causative agents for fungal infections can vary across geographic locations; however, Aspergillus fumigatus and Rhizopus arrhizus are associated with the majority (approximately 70%) of invasive aspergillosis and mucormycosis cases, respectively. Although the epidemiology of rare fungal diseases is not well studied, the incidence rates (per 100,000 persons) for invasive aspergillosis and mucormycosis are estimated to be 4.6 and 0.09 in the UK, 2.8 and 0.04 in Spain, and 1.8 and 0.1 in France, respectively. Incidence rates are difficult to estimate due to a lack of a reliable denominator.*

*Cresemba® (isavuconazole) is an antifungal agent that contains the active substance isavuconazole. Its mechanism of action involves blocking the production of a key component of the cell membrane of fungi, thus weakening the membrane and preventing fungal cell growth. Isavuconazole can be administered orally or by infusion. Isavuconazole was approved by the EMA on October 15, 2015, for use in adults for the treatment of (1) invasive aspergillosis and (2) mucormycosis in patients for whom amphotericin B is inappropriate.*

### 1.2 INVASIVE ASPERGILLOSIS

*Invasive aspergillosis usually occurs in immunocompromised patients with hematological malignancies, oncology patients receiving chemotherapy, and immunosuppressed patients (e.g., as a result of taking immunosuppressive drugs after transplant surgery). Other risk factors include comorbidities such as diabetes, renal or liver dysfunction, chronic obstructive pulmonary disease, and neutropenic sepsis. Patients with comorbidities also are at higher risk for stays in the ICU. Diagnosis of invasive aspergillosis typically is made by the combination of host status, imaging, and mycological findings. Treatment of invasive aspergillosis usually includes antifungal medications such as voriconazole or isavuconazole.*

*The SECURE clinical trial (NCT00412893) was a phase 3, randomized, double-blind, comparative-group study designed to compare the efficacy and safety of isavuconazole vs. voriconazole in the treatment of patients with invasive aspergillosis. The primary outcome measure was all-cause mortality at day 42. In the intention-to-treat population, all-cause mortality was 19% for isavuconazole and 20% for voriconazole, adjusted treatment difference = -1.0% (95% CI: -7.8, 5.7). Patients treated with isavuconazole also had a lower frequency of hepatobiliary disorders (9% vs. 16%; P = 0.016), eye disorders (15% vs. 27%; P = 0.002), and skin or subcutaneous tissue disorders (33% vs.*

PFIZER CONFIDENTIAL

CT24-WI-GL03-RF03 1.0 Non-Interventional Statistical Analysis Plan For Secondary Data Collection  
Study 16-Sep-2020  
Page 5 of 19

42%;  $P = 0.037$ ). Additionally, treatment-related AEs were reported in 42% and 60% of patients receiving isavuconazole and voriconazole, respectively ( $P < 0.001$ ). Guidelines therefore recommend isavuconazole and voriconazole for first-line treatment of invasive aspergillosis.

### 1.3 MUCORMYCOSIS

The main risk factors for mucormycosis include diabetes mellitus, hematological malignancies, stem cell/organ transplantations, corticosteroid therapy, and neutropenia. Mucormycosis usually is diagnosed through identification of causative agents by histopathological analysis of tissue specimens in patients showing symptoms of the infection. However, diagnosis is challenging, and cultures are only occasionally positive. Initial treatment of mucormycosis typically includes surgery to remove infected tissues and antifungal treatment with amphotericin B.

The VITAL clinical trial (NCT00634049) was a single-arm, open-label trial that included an assessment of the efficacy and safety of isavuconazole for treatment of mucormycosis in 37 patients. The primary outcome was independent data review committee-determined overall response (complete or partial response [treatment success] or stable or progressive disease [treatment failure]) at day 42, day 84, and end of treatment. The results demonstrated that by day 42, 11% of patients had a partial response, 43% had stable disease, 3% had disease progression, 8% had missing assessments, and 35% had died. The efficacy of isavuconazole and amphotericin B also was compared in a matched case-control analysis. At day 42, all-cause mortality was similar in cases with isavuconazole as the primary treatment and amphotericin B-treated matched controls (weighted all-cause mortality: 33% vs. 41%;  $P = 0.595$ ).

Although the use of some antifungals are restricted in patients with renal impairment, in a pooled analysis of the SECURE and VITAL trials, isavuconazole was reported to be well tolerated in patients with renal impairment.

### 1.4 STUDY RATIONALE

Isavuconazole obtained market authorization in the US and the EU in 2015. The generation of RWE will provide additional insight into isavuconazole use and related outcomes in clinical practice. The current study is a retrospective cohort study based on a multi-country chart review to be conducted in five European countries (France, Germany, Italy, Spain, and the UK), designed to obtain RWE of isavuconazole patterns of use, clinical response, HCRU, and safety in clinical practice.

## 2 STUDY DESCRIPTION AND OBJECTIVES

### 2.1 STUDY DESCRIPTON

*This is an observational retrospective cohort study involving the review and abstraction of pertinent data from the medical records of patients diagnosed with invasive aspergillosis or mucormycosis who initiated treatment with isavuconazole (index event) between October 15, 2015, and June 30, 2019. The target sample size for this study is approximately 600 patients (with a minimum of 200) across 22 sites located in Europe.*

*De-identified data (i.e., anonymous to nonsite staff) on patient demographics, disease characteristics, isavuconazole treatment patterns, clinical response, safety outcomes, and HCRU will be abstracted from patient medical records and entered into an EDC system between August 2020 and March 2021 for Germany, Spain, and the UK, and between October 2021 and January 2022 for Italy. The differences in the data abstraction timelines are due to ethics and contracting processes in Italy taking between 6 to 12 months to complete, compared with an estimated maximum of 4 months in the remaining countries. As this study is retrospective, information pertaining to patient care will already be documented in patient medical records at the time of medical record abstraction.*

*A steering committee composed of experts within hematology and infectious diseases will provide input and guidance on the study design and implementation, as well as the interpretation of results.*

### 2.2 STUDY OBJECTIVES

#### *Primary Objectives*

- *To document real-world clinical outcomes (all-cause mortality, overall response) of isavuconazole in patients with invasive aspergillosis or mucormycosis receiving treatment in routine clinical practice in Europe*
- *To assess real-world safety (isavuconazole-related AEs and SAEs) of isavuconazole in patients with invasive aspergillosis or mucormycosis receiving treatment in routine clinical practice in Europe*

#### *Secondary Objectives*

- *To describe demographic and clinical characteristics of patients with invasive aspergillosis or mucormycosis receiving isavuconazole in routine clinical practice in Europe*
- *To document treatment patterns among patients with invasive aspergillosis or mucormycosis receiving isavuconazole in routine clinical practice in Europe*
- *To quantify HCRU among patients with invasive aspergillosis or mucormycosis receiving isavuconazole in routine clinical practice in Europe.*

PFIZER CONFIDENTIAL

CT24-WI-GL03-RF03 1.0 Non-Interventional Statistical Analysis Plan For Secondary Data Collection  
Study 16-Sep-2020  
Page 7 of 19

### 3 ANALYSIS POPULATION

The analysis population will consist of adult patients who received isavuconazole for the treatment of invasive aspergillosis or mucormycosis in the hospital setting. Patients who did not receive at least one dose of isavuconazole for treatment of invasive aspergillosis or mucormycosis within the eligibility period will not be considered for analysis.

*Patients must meet all of the following criteria to be eligible for inclusion in the analysis:*

1. *Patient must be aged  $\geq 18$  years at the time of isavuconazole initiation*
2. *Patient must have a record of a diagnosis of invasive aspergillosis or mucormycosis in their medical record at the time isavuconazole was initiated (regardless of whether this diagnosis is suspected or confirmed)*
3. *Patient must have received at least one dose of isavuconazole during the eligibility period (October 15, 2015, to June 30, 2019)*

*All analyses will be performed on the analysis population. Analyses of the primary endpoints may also be performed on up to three subgroups, which will be selected from the following list and determined based on sample size:*

- Neutropenia and non-neutropenia patients
- Patients with central nervous system infections
- Age (e.g.,  $<75$  years vs.  $\geq 75$  years)
- Patients with corticosteroid use at baseline
- Patients with influenza at baseline
- Patients with ICU admission where isavuconazole is initiated
- Patients with history of use of biologics

PFIZER CONFIDENTIAL

[figure not shown]
CT24-WI-GL03-RF03 1.0 *Non-Interventional Statistical Analysis Plan For Secondary Data Collection*  
*Study 16-Sep-2020*  
*Page 8 of 19*

## 4 STUDY DESIGN

### 4.1 SOURCE DATA

The source for all data collected will be patient medical records. Retrospective data will be abstracted from the medical records of patients and entered into an EDC system by trained local site staff. It is estimated that data abstraction will be completed in approximately 7 months from the point at which the first patient is included in the study for Germany, France, Spain, and the UK (estimated to be from August 2020 to March 2021). For Italy, data collection is anticipated to begin at a later date, and data abstraction will be completed in approximately 3 months from the point at which the first patient is enrolled (estimated to be from October 2021 to January 2022).

**Figure 1 Overview of Study Periods and Examples of Eligible Cases**

### 4.2 STUDY PERIODS

[figure not shown]
The index event is defined as the first initiation of isavuconazole treatment for the invasive fungal infection. The index event serves as the point at which (1) a patient

PFIZER CONFIDENTIAL

qualifies for study inclusion, (2) patient follow-up begins, and (3) the patient becomes at risk for experiencing study outcomes. Study periods for data extraction and variable assessment are defined relative to the index event (Figure 1).

- **Eligibility period:** The index date must occur within the eligibility period, which is the timeframe wherein potentially eligible patients are identified for enrolment. *The dates comprising the eligibility period will be October 15, 2015 (date of isavuconazole approval by the EMA in the EU), to June 30, 2019. The end date of the eligibility period ensures that the latest date of isavuconazole initiation will occur at least 6 months before the end of December 2019 (after which point the medical records may contain data related to the COVID-19 pandemic, which is not of interest for this study). This definition will allow for a minimum of 6 months of follow-up from the date of isavuconazole initiation unless the patient dies or is lost to follow-up within this timeframe.*
- **Pre-index period:** *Baseline data on demographics and medical history will be collected based on all available information in medical records before the index event.*
- **Post-index period:** *The timeframe for follow-up data collection will begin one day post-index treatment initiation and end at the earliest of the following: 6 months after post-index treatment discontinuation, death, or loss to follow-up (Figure 1 and Figure 2). Key timepoints of interest for assessment of clinical response and safety will be at 6 weeks, 12 weeks, and 24 weeks after initiation of index treatment (Figure 2).*

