9.4.4. Safety

Category	Variable	Timepoint
AEs	
Type of event (documented by ICD-9 code, ICD-10 code or record in the medical chart):
 
 • Blood and lymphatic AE: 
 • Neutropenia; • Thrombocytopenia; • Pancytopenia; • Leukopenia; • Anemia; • Other (specify). • Immune system AE: 
 • Hypersensitivity; • Other (specify). • Metabolism and nutrition AE: 
 • Hypokalemia; • Decreased appetite; • Hypomagnesemia; • Hypoglycemia; • Hypoalbuminemia; • Malnutrition; • Other (specify). • Psychiatric AE: 
 • Delirium; • Depression; • Insomnia; • Other (specify); • Nervous system AE: 
 • Headache; • Somnolence; • Convulsion; 	Index date, post-index period

Category	Variable	Timepoint
	
 • Syncope; • Dizziness; • Paresthesia; • Encephalopathy; • Presyncope; • Peripheral neuropathy; • Dysgeusia; • Other (specify). • Ear and labyrinth AE: 
 • Vertigo; • Other (specify). • Cardiac AE: 
 • Atrial fibrillation; • Tachycardia; • Bradycardia; • Palpitations; • Atrial flutter; • Electrocardiogram QT shortened; • Supraventricular tachycardia; • Ventricular extrasystoles; • Supraventricular extrasystoles; • Other (specify). • Vascular AE: 
 • Thrombophlebitis; • Circulatory collapse; • Hypotension; • Other (specify). • Respiratory, thoracic and mediastinal AE: 
 • Dyspnea; • Acute respiratory failure; • Bronchospasm; • Tachypnoea; • Hemoptysis; • Epistaxis; • Other (specify). • Gastrointestinal AE: 
 • Vomiting; • Diarrhea; • Nausea; • Abdominal pain; 	

Category	Variable	Timepoint

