9.4.5. Survival Status

Category	Variable	Timepoint
Survival status	
Date of death (DD MMM YYYY)
 
Primary cause of death:
 
 • Complications related to invasive aspergillosis or mucormycosis; • Other disease complications; • SAE related to isavuconazole treatment; • SAE unrelated to isavuconazole treatment; • Other (specify); • Unknown. 	Post-index period

SAE = serious adverse event.

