**Table 1      Outcome Definitions**

Variable	Definition	Timepoint
Death	Death as indicated on the medical record abstraction form.	Post-index period
Clinical response	
Clinical success: Resolution or partial resolution of all attributable clinical symptoms and physical findings.
 
Clinical failure: No resolution of any attributable clinical symptoms and physical findings and/or worsening.
 
When medical record documentation is not clear to the abstractor as to which category should be specified, the investigator should review all available medical record documentation to determine classifications. If the investigator determines there is not enough medical record documentation to make the classification, he or she will indicate that the response is 'unknown'. Since clinical response classification is important to the study, participating sites will be selected for participation in the study based on their reporting whether they have enough medical record documentation to classify the response.
	Post-index period
Radiological response	
Radiological success: <math>\geq 50\%</math> improvement from initial assessment or improvement of at least 25% from the initial assessment for the follow-up at 6 weeks (i.e., day 42 [<math>\pm 14</math> days]) or if end of treatment occurred before this time.
 
Radiological failure: Failure to meet success criteria.
	Post-index period

PFIZER CONFIDENTIAL

CT24-WI-GL03-RF03 1.0 *Non-Interventional Statistical Analysis Plan For Secondary Data Collection*  
*Study 16-Sep-2020*  
 Page 11 of 19

Variable	Definition	Timepoint
	When medical record documentation is not clear enough for the abstractor as to which category should be specified, the investigator should review all available medical record documentation to determine classifications. If the investigator determines there is not enough medical record documentation to make the classification, he or she will indicate that the response is 'unknown.' Since radiological response classification is important to the study, participating sites will be selected for participation in the study based on their reporting whether they have enough medical record documentation to classify the response.	

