Mycological response	
Mycological success will be defined as eradication or presumed eradication of the original causative organism cultured.
 
Mycological failure will be defined as persistence or presumed persistence.
 
When medical record documentation is not clear to the abstractor as to which category should be specified, the investigator should review all available medical record documentation to determine classifications. If the investigator determines there is not enough medical record documentation to make the classification, he or she will indicate that the response is 'unknown.' Since mycological response classification is important to the study, participating sites will be selected for participation in the study based on their reporting whether they have enough medical record documentation to classify the response.
	Post-index period

PFIZER CONFIDENTIAL

CT24-WI-GL03-RF03 1.0 *Non-Interventional Statistical Analysis Plan For Secondary Data Collection*  
 Study 16-Sep-2020  
 Page 12 of 19

Variable	Definition	Timepoint
Adverse events	Documentation of any adverse event in the medical record or as described by the ICD-9 or ICD-10 systems.	Post-index period
Serious adverse event	Documentation of any serious adverse event in the medical record or as described by the ICD-9 or ICD-10 systems.	Post-index period
Treatment patterns	Documentation of any of the following in the medical record: 
 
• Index treatment modification
 
• Index treatment discontinuation
 
• TDM
 
• Switching to a new antifungal therapy after index treatment discontinuation
 
• Use of subsequent antifungal therapy after end of index treatment
 
• Index treatment administered as part of antifungal combination therapy
 
• Other concomitant treatments not including combination antifungal therapy
 
• Index treatment administered in the outpatient setting following initiation in the inpatient setting
 
	Post-index period
Healthcare resource utilization	Documentation of any inpatient stay (including specialty wards, ICU, ER, general medicine ward, or other) or outpatient visit (not associated with a hospitalization) in the medical record.	Post-index period

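### SAP Table 1 limits AEs and SAEs to a period starting the day after initiation, whereas protocol 9.4.4 includes the index date; the two should be reconciled

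*SAP*

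**What the plan says.** SAP section 5 makes Table 1 the place where outcomes are defined. Table 1 defines an AE as "Documentation of any adverse event in the medical record or as described by the ICD-9 or ICD-10 systems" and an SAE as "Documentation of any serious adverse event in the medical record or as described by the ICD-9 or ICD-10 systems". For both, the timepoint column names the post-index period and nothing else.

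SAP 4.2 fixes the start of that period: "The timeframe for follow-up data collection will begin one day post-index treatment initiation". A few lines earlier, the same section describes the index event as the point at which "2) patient follow-up begins, and (3) the patient becomes at risk for experiencing study outcomes".

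Protocol 9.3.1.3 also starts the post-index period one day after initiation. In protocol 9.4.4, however, the AE timepoint is "Index date, post-index period", so the index date is named as well as the later period.

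For deaths the two documents agree. Protocol 9.4.5 lists survival status under "Post-index period", and SAP Table 1 uses the same period, with the definition "Death as indicated on the medical record abstraction form".

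**The concern.** Isavuconazole-related AEs and SAEs are a primary objective. Protocol 9.9.2.1 leaves the definitions of AE and SAE to the SAP, and the SAP puts them in Table 1. A timepoint in that table therefore decides which events count.

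The table omits the index date, which the protocol includes for AEs, and gives no reason. It also conflicts with the SAP's own statement of when risk begins. Two programmers working in good faith could produce different primary safety tables: one following Table 1 and dropping onsets dated on the index date, the other following the at-risk statement and keeping them.

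The affected day is the day of first exposure. Protocol 9.9 also says that major changes to primary outcome definitions should be reflected in a protocol amendment, and protocol section 5 records none. If the narrower window is intended, it needs at least a stated reason. If it is not, the table needs correcting.

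**Working it through.** **Step 1. Set the windows side by side** (day 0 = index date).

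| Source | Item | First day covered |
|---|---|---|
| Protocol 9.3.1.3 | Post-index period | Day 1 |
| Protocol 9.4.4 | AEs | Day 0, because the index date is named separately |
| SAP 4.2 | Post-index period | Day 1 |
| SAP 4.2 | Start of follow-up and risk | Day 0 |
| SAP Table 1 | AEs, SAEs | Day 1 |
| SAP 6.4 | AE tables, time to first AE | No lower limit stated |
| Protocol 9.4.5, SAP Table 1 | Death | Day 1 in both |
| SAP 6.3 | Death in Kaplan-Meier | Any documented death, time measured from day 0 |

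The protocol's post-index period starts on day 1, so naming the index date in 9.4.4 adds a day. The protocol makes this distinction elsewhere: treatment setting, combination therapy and biomarkers carry the index date, while treatment modification and discontinuation do not. The addition for AEs therefore looks deliberate.

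**Step 2. Dosing on the omitted day.** Protocol 9.4.2 lists one loading option of a dose every 8 hours for 48 hours: 48 / 8 = 6 doses. With the first dose at clock hour h, doses fall at h, h + 8, h + 16 and so on. The number before midnight of the index date is:
- h from 0 to 7: 3 doses
- h from 8 to 15: 2 doses
- h from 16 to 23: 1 dose

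So 1, 2 or 3 of the 6 doses fall on the index date, each for 8 of the 24 possible start hours. The form also allows another schedule, to which this count does not apply.

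**Step 3. Direction of the effect.** Table 1 removes events, not patients; the analysis population in SAP section 3 is unchanged. A patient whose only AE began on day 0 moves from yes to no, and a patient with a later AE stays at yes. The proportion with any AE can therefore fall or stay the same, but cannot rise. For time to first AE, each affected patient's event is replaced by a later event or by censoring.

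**Step 4. Size.** The documents give no index-date event rate. If a share f of N patients had their only AE on the index date, N × f patients would change category and the proportion would fall by f. For illustration only, with f assumed:

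| f (assumed) | N = 200 (stated minimum) | N = 600 (target) |
|---|---|---|
| 0.5% | 1 | 3 |
| 1% | 2 | 6 |
| 2% | 4 | 12 |

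Nothing in the documents favours one row over another.

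**Step 5. Time-0 events.** SAP 6.1 computes times as date differences, so an index-date AE has time 0. SAP 6.4 does not say how such events enter the analysis.

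**The case against.** The strongest reply is that the SAP does not clearly exclude these events. SAP 4.2 puts patients at risk from the index event. SAP 6.4, which specifies the safety analysis, has no lower date limit. The table shells are in an attached spreadsheet, and Figures 1 and 2 are not visible in the text reviewed; either could settle the window. This stands in part. A reader might infer that index-date AEs are certain to be dropped, but the documents support only a contradiction in which the governing table points towards exclusion. Silence in 6.4 does not override an explicit timepoint in Table 1.

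A reader might also infer that deaths are lost from the primary safety analysis. That is not supported. All-cause mortality belongs to the clinical-outcomes objective, protocol and SAP give it the same timepoint, and SAP 6.3 counts any documented death as the event.

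A third inference is that the rule selectively removes reactions to first exposure. The AE list in protocol 9.4.4 does include hypersensitivity, bronchospasm and injection site reaction, but the documents do not say when such events occur.

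Finally, counting the index date has a cost. Dosing and AE onset are recorded by date without clock time, so an event that began before the first dose cannot be told apart by timing. This stands, and it rules out an after-first-dose qualifier based on these fields.

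**Conclusion.** The discrepancy for AEs and SAEs is real and concerns a primary objective. Table 1 as written leaves out the index date, against protocol 9.4.4 and against the at-risk statement in SAP 4.2. If it is followed, the proportion of patients with an AE or SAE can only fall or stay the same. The amount cannot be derived from the documents, and any patient count rests on an assumed index-date rate. For deaths there is no difference between protocol and SAP, only a loose end between Table 1 and SAP 6.3.

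The conclusion assumes that Table 1 governs, as SAP section 5 says, and that the unseen shells and figures do not already restore the index date. It is worth correcting because the change is nearly free and determines which events count.

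**What to change.** - In SAP Table 1, set the timepoint for AEs and SAEs to the index date plus the post-index period, as in protocol 9.4.4.
- In SAP 6.4, state that onsets on the index date count in the week 6, 12 and 24 tables and enter the Kaplan-Meier analysis as events at time 0. Shifting them to a small positive time is an optional convention and is not needed.
- Note in the SAP that some index-date events may have begun before the first dose. Use the documented relationship to isavuconazole, already collected under protocol 9.4.4, to present drug-related events separately. Where that field is unknown, the uncertainty remains and should be reported.
- Add one line that deaths on the index date count, consistent with SAP 6.3.
- Check that the table shells use the same window.

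The cost is SAP wording and a check of the shells. The protocol already has index-date AEs abstracted, so no new data field is needed. The one drawback is the possible inclusion of a few pre-dose events. If the narrower window is in fact intended, the SAP should say why, and the sponsor should consider whether protocol 9.9 calls for an amendment.
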